**Table 10. Schedule of Assessments (Cohort 1) – Off-treatment Follow-Up for Subjects Meeting Treatment Stopping Criteria**

Study Day or Week	Wk 50	Wk 52	Wk 54	Wk 56	Wk 60	Wk 64	Wk 68	Wk 72	Wk 76	Wk 80	Wk 84	Wk 88	Wk 92	Wk 96
Visit Windows (days)	±5	±5	±5	±5	±5	±5	±5	±5	±5	±5	±5	±5	±5	±5
Weight								X						X
Vital signs	X	X	X	X	X	X	X	X	X	X	X	X	X	X
Complete physical exam								X						X
Symptom-directed physical exam	X	X	X	X	X	X	X	X	X	X	X	X	X	
12-lead ECG a					X									X
Review of concomitant medications & AEs	X	X	X	X	X	X	X	X	X	X	X	X	X	X
Fibroscan ® (if available)								X						X
FibroTest ® , APRI								X						X
Chemistry, hematology, coagulation	X	X	X	X	X	X	X	X	X	X	X	X	X	X
CrCl								X						X
Pregnancy test b	X	X	X	X	X	X	X	X	X	X	X	X	X	X
Urinalysis	X	X	X	X	X	X	X	X	X	X	X	X	X	X
HBV DNA (COBAS ® TaqMan ® )	X	X	X	X	X	X	X	X	X	X	X	X	X	X
HBV RNA (COBAS ® )	X	X	X	X	X	X	X	X	X	X	X	X	X	X
HBV TNA	X	X	X	X	X	X	X	X	X	X	X	X	X	X
Qualitative HBeAg					X			X			X			X
HBeAb					X			X			X			X
Quantitative HBsAg c	X	X	X	X	X	X	X	X	X	X	X	X	X	X
HBcrAg					X			X			X			X
HBsAg isoforms	X	X	X	X	X	X	X	X	X	X	X	X	X	X
Immune complexes		X		X	X	X		X			X			X
Sample for HBV resistance monitoring	X	X	X	X	X	X	X	X	X	X	X	X	X	X
Virology back-up sample d	X	X	X	X	X	X	X	X	X	X	X	X	X	X
Immune biomarkers/cytokines				X		X		X			X			X
PBMCs e				X		X		X			X			X
RNAi biomarker sample	X	X	X	X	X	X	X	X	X	X	X	X	X	X
Sparse PK of VBR (off-treatment; Groups 1, 2)	X													

Vebicorvir

ABI-H0731-204 Protocol Amendment 1 27 October 2021

Study Day or Week	Wk 50	Wk 52	Wk 54	Wk 56	Wk 60	Wk 64	Wk 68	Wk 72	Wk 76	Wk 80	Wk 84	Wk 88	Wk 92	Wk 96
Visit Windows (days)	±5	±5	±5	±5	±5	±5	±5	±5	±5	±5	±5	±5	±5	±5
VBR Accountability (Groups 1, 2) f	X													

Abbreviations: Ab=antibody; AE=adverse event; APRI=aspartate aminotransferase to platelet ratio index; CrCl=creatinine clearance; DNA=deoxyribonucleic acid; ECG=electrocardiogram; HBcrAg=hepatitis B core-related antigen; HBeAb=anti-hepatitis B e antigen antibody; HBeAg=hepatitis B e antigen; HBsAg=hepatitis B surface antigen; NrtI=nucleos(t)ide/reverse transcriptase inhibitor; PK=pharmacokinetic(s); RNA=ribonucleic acid; TNA=total nucleic acids; UV=Unscheduled visit; Wk(s)=week(s); VBR=vebicorvir.

- a Any clinically significant ECG result will be confirmed.
- b Pregnancy tests may be conducted by urine dipstick. If positive on dipstick, reflex to serum.
- c If quantitative HBsAg is <LLOQ, then reflex to qualitative HBsAg. HBsAb is performed at Screening, Day 1, and Week 48. Additionally, if HBsAg is <LLOQ then reflex testing of HBsAb will also be performed.
- d The virology back-up sample will be used for retesting the specified HBV parameters.
- e PBMC collection at selected sites only; not to be collected at subsequent timepoints if not collected at Day 1.
- f Subjects will either stop their treatment altogether or continue with NrtI administration based on assessment of Treatment Stopping Criteria (Section 4.1.1) utilizing laboratory results from the Week 48 Visit. Subjects will remain on assigned oral agents (ie, VBR+NrtI for groups 1 and 2, and NrtI for Group 3) beyond the Week 48 visit until all laboratory results are available to adjudicate the Treatment Stopping Criteria.

**Table 11. Schedule of Assessments (Cohort 1) – Follow-up for Rest of the Subjects**

Study Day or Week	Wk 52	Wk 56	Wk 60	Wk 64	Wk 68	Wk 72	Wk 76	Wk 80	Wk 84	Wk 88	Wk 92	Wk 96
Visit Windows (days)	±5	±5	±5	±5	±5	±5	±5	±5	±5	±5	±5	±5
Weight						X						X
Vital signs	X	X	X	X	X	X	X	X	X	X	X	X
Complete physical exam						X						X
Symptom-directed physical exam	X	X	X	X	X		X	X	X	X	X	
12-lead ECG a			X									X
Review of concomitant medications & AEs	X	X	X	X	X	X	X	X	X	X	X	X
Fibroscan ® (if available)						X						X
FibroTest ® , APRI						X						X
Chemistry, hematology, coagulation	X	X	X	X	X	X	X	X	X	X	X	X
CrCl						X						X
Pregnancy test b	X	X	X	X	X	X	X	X	X	X	X	X
Urinalysis	X	X	X	X	X	X	X	X	X	X	X	X
HBV DNA (COBAS ® TaqMan ® )			X			X			X			X

Vebicorvir

ABI-H0731-204 Protocol Amendment 1 27 October 2021

Study Day or Week	Wk 52	Wk 56	Wk 60	Wk 64	Wk 68	Wk 72	Wk 76	Wk 80	Wk 84	Wk 88	Wk 92	Wk 96
Visit Windows (days)	±5	±5	±5	±5	±5	±5	±5	±5	±5	±5	±5	±5
HBV RNA (COBAS®)	X	X	X	X	X	X	X	X	X	X	X	X
HBV TNA	X	X	X	X	X	X	X	X	X	X	X	X
Qualitative HBeAg			X			X			X			X
HBeAb			X			X			X			X
Quantitative HBsAg c	X	X	X	X	X	X	X	X	X	X	X	X
HBcrAg			X			X			X			X
HBsAg isoforms	X	X	X	X	X	X	X	X	X	X	X	X
Immune complexes	X	X	X	X		X			X			X
Sample for HBV resistance monitoring	X	X	X	X	X	X	X	X	X	X	X	X
Virology back-up sample d	X	X	X	X	X	X	X	X	X	X	X	X
Immune biomarkers/cytokines		X		X		X			X			X
PBMCs e		X		X		X			X			X
RNAi biomarker sample	X	X	X	X	X	X	X	X	X	X	X	X
NrtI administration (see Sections 4.1.1, 4.1.2)	X	X	X	X	X	X	X	X	X	X	X	X
Review subject dosing diary	X	X	X	X	X	X	X	X	X	X	X	X
Sparse PK of VBR (Groups 1, 2)	X											
VBR accountability (Groups 1, 2) f	X											

Abbreviations: Ab=antibody; AE=adverse event; APRI=aspartate aminotransferase to platelet ratio index; CrCl=creatinine clearance; DNA=deoxyribonucleic acid; ECG=electrocardiogram; HBcrAg=hepatitis B core-related antigen; HBeAb=anti-hepatitis B e antigen antibody; HBeAg=hepatitis B e antigen; HBsAg=hepatitis B surface antigen; NrtI=nucleos(t)ide/reverse transcriptase inhibitor; PK=pharmacokinetic(s); RNA=ribonucleic acid; TNA=total nucleic acids; UV=Unscheduled visit; Wk(s)=week(s); VBR=vebicorvir.

a Any clinically significant ECG result will be confirmed.

b Pregnancy tests may be conducted by urine dipstick. If positive on dipstick, reflex to serum.

c If quantitative HBsAg is <LLOQ, then reflex to qualitative HBsAg. HBsAb is performed at Screening, Day 1, and Week 48. Additionally, if HBsAg is <LLOQ then reflex testing of HBsAb will also be performed.

d The virology back-up sample will be used for retesting the specified HBV parameters.

e PBMC collection at selected sites only; not to be collected at subsequent timepoints if not collected at Day 1.

f Subjects will either stop their treatment altogether or continue with NrtI administration based on assessment of Treatment Stopping Criteria (Section 4.1.1) utilizing laboratory results from the Week 48 Visit. Subjects will remain on assigned oral agents (ie, VBR+NrtI for groups 1 and 2, and NrtI for Group 3) beyond the Week 48 visit until all laboratory results are available to adjudicate the Treatment Stopping Criteria.

## 8.2 Study Visit Assessments

To reduce the risk of potential exposure to COVID-19, study visits may be conducted by home health personnel in the home of the subject and study drug may be shipped by courier directly from the study site to the subject or provided via other alternative mechanisms of provision. Subjects must provide prior consent (verbal or written) for home visits and direct shipment of study drug to their home. Telemedicine visits may be allowed if the clinical site or subject is directly affected by local COVID restrictions. Blood sampling for telemedicine visits may be drawn by home health personnel or via subject visit to a local laboratory.

## 8.3 Subject Enrollment and Treatment Assignment

Following provision of informed consent and completion of all Screening and Day 1 assessments, if a subject meets all protocol eligibility requirements the Investigator or designee will randomize the subject using the IRT system described in [Section 6.4.1](#) and [Table 7](#). Protocol waivers will not be granted for any reason.

### 8.3.1 Screening Visits

The following Screening assessments must be completed within 45 days of the scheduled Day 1 visit:

- Obtain written informed consent prior to the initiation of any Screening procedures
- Record demographics and medical history, including HBV history
- Measure height and weight
- Record vital signs (temperature, heart rate, respiration rate, and blood pressure)
- Complete physical examination (excluding breast and genitalia, unless indicated)
- 12-lead ECG
- Review of concomitant medications
- Review of AEs occurring after provision of informed consent
- Liver staging (via FibroScan (if available)/other Sponsor-approved hepatic imaging method OR via liver biopsy)
- FibroTest®, APRI
- Obtain blood samples for the following:
  - Safety laboratory tests: chemistry, hematology, coagulation, CrCl

- Virology: HBV genotype sample, HBV total nucleic acids (TNA), HBV DNA, HBV RNA, HBsAg, qualitative HBeAg, HBsAb, HBeAb, HBsAg isoforms and immune complexes, HBcrAg, HBV resistance monitoring sample
- Virology back-up sample (to be used for retesting HBV parameters)
- Serology: HAV, HCV, hepatitis D virus (HDV), hepatitis E virus (HEV), HIV
- Other: AFP, glycated hemoglobin (HbA1c), pregnancy test for female subjects of child-bearing potential
- Obtain urine sample for:
  - Urine drug test
- Confirm subject eligibility

### 8.3.2 Day 1 Visit

The following procedures must be completed at Day 1, prior to the first dose of study drug:

- Update medical history, including HBV history
- Measure weight
- Vital signs (temperature, heart rate, respiration rate, and blood pressure)
- Complete physical examination
- 12-lead ECG
- Review AEs and concomitant medications
- Obtain blood samples for the following:
  - Safety laboratory tests: chemistry, hematology, coagulation, CrCl
  - Virology: HBV TNA, HBV DNA, HBV RNA, HBsAg, HBeAg, HBsAb, HBeAb, HBsAg isoforms and immune complexes, HBcrAg, HBV resistance monitoring sample
  - Virology back-up sample (to be used for retesting HBV parameters)
  - Other:
    - Pregnancy test for female subjects of child-bearing potential
    - Sparse PK samples for VBR and NrtI

- Sparse PK samples for AB-729 at 2 hours ( $\pm 1$  hour) postdose (for subjects who are not participating in the AB-729 optional intensive PK substudy only)
  - Blood samples for AB-729 intensive PK substudy (optional) will be collected at the timepoints listed in [Section 8.8.5](#)
  - Cytokines/Immune biomarkers
  - PBMCs (at selected sites only)
  - RNAi biomarker
- Obtain urine samples for the following:
    - Pregnancy test for female subjects of child-bearing potential
    - Urinalysis
  - Confirm subject eligibility
  - Complete randomization (IRT)
  - IMP (VBR and AB-729) and NIMP (NrtI) administration during clinic visit
  - Dispense VBR bottles
  - Provide dosing diary to the subject and record first dose administration
  - Provide injection site reaction diary for subjects in Groups 1 and 3

### 8.3.3 Week 2 Through Week 48 Visits ( $\pm 3$ Days)

The following assessments will be performed at Study Weeks 2, 4, 8, 12, 16, and every 4 weeks thereafter through Week 48 (inclusive) unless otherwise indicated:

- Measure body weight (Weeks 24 and 48 only)
- Record vital signs (temperature, heart rate, respiration rate and blood pressure)
- Complete physical examination (excluding breast and genitalia, unless indicated; Weeks 24 and 48 only); all other visits, symptom-directed physical examination
- 12-lead ECG (Weeks 12, 24, 36, and 48 only)
- FibroScan (if available; Weeks 24 and 48 only)
- Review AEs and concomitant medications

- Obtain blood samples for the following:
  - Safety laboratory tests:
    - chemistry, hematology, coagulation
    - CrCl (Weeks 24 and 48 only)
  - Virology:
    - HBV TNA, HBV RNA, HBsAg, HBsAb (only if HBsAg <LLOQ), HBsAg isoforms and immune complexes, HBV resistance monitoring sample
    - HBV DNA (at Weeks 12, 24, 36, and 48 only)
    - HBeAg, HBeAb, HBsAb, HBcrAg (at Week 48 only)
    - Virology back-up sample (to be used for retesting HBV parameters)
  - Other:
    - FibroTest, APRI (both at Weeks 24 and 48 only)
    - Sparse PK samples for VBR and NrtI
    - Sparse PK samples for AB-729 at 2 hours ( $\pm 1$  hour) postdose (at Weeks 8, 16, 24, and 32 only) and also at Week 40 from subjects who are not participating in the optional intensive PK substudy
    - Blood samples for AB-729 intensive PK substudy (optional) will be collected after the last dose (at Week 40 only) at the timepoints listed in [Section 8.8.5](#)
    - Cytokines/Immune biomarkers (at Weeks 2, 4, 8, 12, 20, 28, 36, and 44 only)
    - PBMCs (at selected sites at Weeks 2, 4, 8, 12, 20, 28, 36, and 44 only; not to be collected at subsequent timepoints if not collected at Day 1)
    - RNAi biomarker
    - Pharmacogenomics sample (optional, at Week 16 only); collected only in subjects who provide additional informed consent and can be collected at a later visit if not collected at Week 16
- Obtain urine samples for the following:
  - Pregnancy test for female subjects of child-bearing potential
  - Urinalysis

- Review subject injection site reaction diary (Groups 1 and 3) at Weeks 2, 12, 20, 28, 36, and 44
- Subject dosing diary
- Assess VBR accountability (Groups 1 and 2)
- Dispense VBR bottles (excluding Week 2); final dispensation at Week 44
- Assessment of Treatment Stopping Criteria (see [Section 4.1.1](#) for details)
- VBR and NrtI administration once daily at home; Subjects will continue to receive VBR and NrtI beyond the Week 48 visit, until all laboratory results are available to adjudicate individual subject Treatment Stopping Criteria (see [Section 4.1.1](#)).
- AB-729 administration in clinic at Weeks 8, 16, 24, 32, and 40; last administration of AB-729 at Week 40

#### **8.3.4 Week 50 Through Week 96 Off-Treatment Follow-Up Visits for Subjects Meeting Treatment Stopping Criteria ( $\pm 5$ Days)**

The following follow-up assessments will be performed from Study Weeks 50 through 96 for subjects meeting Treatment Stopping Criteria (see [Table 10](#)). Note: If a subject is determined to meet the NrtI-restart criteria at any time during the follow-up, he/she should follow the schedule of visits specified in [Section 8.3.5](#) and [Table 11](#):

- NrtI and VBR will continue to be administered at home until laboratory results from the Week 48 visits are available to determine if an individual subject meets Treatment Stopping Criteria (see [Section 4.1.1](#)). Once a subject meets the Treatment Stopping Criteria and is notified by the site, subject will discontinue treatment with NrtI and VBR.
- Measure body weight (Weeks 72 and 96 only)
- Record vital signs (temperature, heart rate, respiration rate, and blood pressure)
- Complete physical examination (excluding breast and genitalia, unless indicated; Week 72 and 96 only); all other visits, symptom-directed physical examination
- 12-lead ECG (Weeks 60 and 96 only)
- Review AEs and concomitant medications
- FibroScan (if available; Weeks 72 and 96 only)
- Obtain blood samples for the following:
  - Safety laboratory tests:

- chemistry, hematology, coagulation
- CrCl (Weeks 72 and 96 only)
- Virology:
  - HBV DNA, HBV TNA, HBV RNA
  - HBsAg, HBsAb (only if HBsAg <LLOQ), HBsAg isoforms, HBV resistance monitoring sample
  - Immune complexes (Weeks 52, 56, 60, 64, 72, 84, and 96 only)
  - HBeAg, HBeAb, HBcrAg (Weeks 60, 72, 84, and 96 only)
  - Virology back-up sample (to be used for retesting HBV parameters)
- Other:
  - FibroTest, APRI (both at Week 72 and 96 only)
  - A single off-treatment blood sample for sparse PK of VBR (Groups 1 and 2; Week 50 only)
  - Cytokines/Immune biomarkers (Weeks 56, 64, 72, 84, and 96 only)
  - PBMCs (at selected sites at Weeks 56, 64, 72, 84, and 96; not to be collected at subsequent timepoints if not collected at Day 1)
  - RNAi biomarker
- Obtain urine samples for the following:
  - Pregnancy test for female subjects of child-bearing potential
  - Urinalysis
- VBR accountability (Groups 1 and 2; Week 50 only)

### **8.3.5 Week 52 Through Week 96 Follow-Up Visits for Rest of the Subjects (±5 Days)**

The following follow-up assessments will be performed every 4 weeks from Study Weeks 52 through 96, for subjects who do NOT meet the Treatment Stopping Criteria, or subjects who meet the NrtI-restart criteria after having met Treatment Stopping Criteria, or subjects who prematurely discontinue treatment with VBR/AB-729 at any time (see [Table 11](#)):

- NrtI and VBR will continue to be administered at home until laboratory results from the Week 48 visits are available to adjudicate the individual subject Treatment Stopping Criteria (see [Section 4.1.1](#)). Once a subject is determined to not meet the Treatment Stopping Criteria, he/she will be notified by the site, and the subject will discontinue treatment with VBR.
- NrtI administration once daily at home through Week 96
- Measure body weight (Weeks 72 and 96 only)
- Record vital signs (temperature, heart rate, respiration rate, and blood pressure)
- Complete physical examination (excluding breast and genitalia, unless indicated; Week 72 and 96 only); all other visits, symptom-directed physical examination
- 12-lead ECG (Weeks 60 and 96 only)
- Review AEs and concomitant medications
- FibroScan (if available; Weeks 72 and 96 only)
- Obtain blood samples for the following:
  - Safety laboratory tests:
    - chemistry, hematology, coagulation
    - CrCl (Weeks 72 and 96 only)
  - Virology:
    - HBV TNA, HBV RNA
    - HBV DNA (Weeks 60, 72, 84, and 96 only)
    - HBsAg, HBsAb (only if HBsAg <LLOQ), HBsAg isoforms, HBV resistance monitoring sample
    - Immune complexes (Weeks 52, 56, 60, 64, 72, 84, and 96 only)
    - HBeAg, HBeAb, HBcrAg (Weeks 60, 72, 84, and 96 only)
    - Virology back-up sample (to be used for retesting HBV parameters)
  - Other:
    - FibroTest, APRI (both at Week 72 and 96 only)

- A single off-treatment blood sample for sparse PK of VBR (Groups 1 and 2; Week 52 only)
- Cytokines/Immune biomarkers (Weeks 56, 64, 72, 84, and 96 only)
- PBMCs (at selected sites at Weeks 56, 64, 72, 84, and 96; not to be collected at subsequent timepoints if not collected at Day 1)
- RNAi biomarker
- Obtain urine samples for the following:
  - Pregnancy test for female subjects of child-bearing potential
  - Urinalysis
- Subject dosing diary
- VBR accountability (Groups 1 and 2; Week 52 only)

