#### 4.1.2 NrtI-Restart Criteria

Subjects who meet the Treatment Stopping Criteria at the Week 48 assessment but subsequently meet **ANY** of the below NrtI-Restart Criteria, will restart treatment with NrtI and remain in follow-up through Week 96.

NrtI-Restart Criteria are:

- ALT > 10 ×ULN, confirmed by repeat
- ALT > Baseline and > ULN, confirmed by repeat, and
  - Direct bilirubin > 2.0 × ULN, confirmed by repeat, or
  - International Normalized Ratio > 1.5, confirmed by repeat
- ALT ≥ 2 – 5 × ULN AND HBV DNA > 2000 IU/mL for 12 weeks
- ALT elevations ≥ 5 – 10 ×ULN AND HBV DNA > 2000 IU/mL for 4 weeks
- Any clinical decompensation, regardless of HBV DNA level
- Investigator discretion

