#### **8.4 Unscheduled Visit**

An unscheduled visit may be performed at any time at the discretion of Investigator in order to further evaluate a subject. The specific assessments to be performed at these visits would be determined by the Investigator according to nature of the subject specific follow-up required, however at a minimum the assessments would include the following:

- Record vital signs (temperature, heart rate, respiration rate, and blood pressure)
- Symptom-directed physical examination
- Review AEs and concomitant medications
- Obtain blood samples for the following, as applicable:
  - Safety laboratory tests: chemistry, hematology, coagulation, CrCl
  - Virology: HBV TNA, HBV DNA, HBV RNA, HBsAg, HBsAg isoforms and immune complexes, HBV resistance monitoring sample
  - Virology back-up sample (to be used for retesting HBV parameters)
  - Other:
    - Sparse PK sample for VBR and NrtI
    - Cytokines/immune biomarkers

- PBMCs (at selected sites, if feasible)
- RNAi biomarker
- Obtain urine samples, as applicable for:
  - Pregnancy test for female subjects of child-bearing potential
  - Urinalysis
- Assess VBR accountability and review subject dosing diary, as applicable

Assessments performed should be documented in the subject's source documentation. Clinical laboratory assessments should be conducted through the central laboratory. The minimum Unscheduled Visit assessments to be completed when managing ALT elevations are noted in [Section 9.10.4](#).

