#### **9.10.4 Management of Alanine Aminotransferase (ALT) Elevations**

All subjects participating in the study will be closely monitored for ALT elevations and/or signs of potential decline in hepatic function (see [Figure 7](#)). Subjects experiencing ALT elevations  $\geq 2\times$  Baseline (Day 1) or on-treatment nadir and  $>2\times$  ULN during study treatment or during post-treatment follow-up should be closely monitored with regular Unscheduled Visits every 1 to 2

weeks at the discretion of the Investigator. At these visits, the following laboratory tests will be performed: ALT, AST, total bilirubin (if total bilirubin is elevated, reflex to direct bilirubin), serum albumin, INR and creatine kinase. The Investigator will determine if other Unscheduled Visit assessments should be performed. Additionally, the following guidance is provided for management of subjects with ALT elevations:

- ALT Elevation Without Declining Hepatic Function
  - All subjects with an ALT elevation on treatment, defined as ALT  $>2\times$  Baseline or on treatment nadir and  $\geq 10\times$  ULN, should have the ALT findings confirmed within 3 days of receipt of the original results. All subjects should return for an Unscheduled Visit.
  - If the ALT elevation is confirmed, then an additional Unscheduled Visit will be performed to further evaluate the subject. At this visit, the following laboratory tests will be performed: ALT, AST, total bilirubin (if total bilirubin is elevated, reflex to direct bilirubin), serum albumin, INR, creatine kinase, HBV DNA, quantitative HBV serologies (HBeAg [reflex qualitative HBeAg if quantitative HBeAg is negative] and HBsAg [reflex qualitative HBsAg if quantitative HBsAg is negative]), HAV immunoglobulin M (IgM), HCV RNA, HDV RNA, HEV IgM, ANA, smooth muscle antibodies and anti-LKM1 antibodies, EBV DNA, CMV DNA, HSV DNA, and total IgG. The Investigator will determine if other Unscheduled Visit assessments should be performed.
    - If an intercurrent illness is determined to be causal, subjects with an ALT elevation without declining hepatic function and without contraindications may continue treatment and the intercurrent illness should be treated as deemed medically appropriate by the Investigator.
    - Subjects with an ALT elevation without declining hepatic function and without contraindications may continue treatment with study drug under close observation.

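### After NrtI restart, scheduled HBV DNA drops from every visit to four fixed study weeks, so the first post-restart sample can be up to 12 weeks away

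*Combined protocol and SAP*

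**What the plan says.** **Off treatment.** Protocol Section 8.3.4 lists "HBV DNA, HBV TNA, HBV RNA" with no restriction by week. Table 10 marks HBV DNA at all 14 visits: Weeks 50, 52, 54, 56, 60, then every 4 weeks to Week 96.

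**On restart.** Section 8.3.4 says: "If a subject is determined to meet the NrtI-restart criteria at any time during the follow-up, he/she should follow the schedule of visits" set out in Section 8.3.5 and Table 11. Section 8.3.5 names restarters among the subjects it covers. Its visits are 4-weekly by study week, but for HBV DNA it says "HBV DNA (Weeks 60, 72, 84, and 96 only". The Table 11 row agrees: 4 of 12 visits.

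**Who restarts.** Two criteria in Section 4.1.2 are defined by HBV DNA: "ALT ≥ 2 – 5 × ULN AND HBV DNA > 2000 IU/mL for 12 weeks" and "ALT elevations ≥ 5 – 10 ×ULN AND HBV DNA > 2000 IU/mL for 4 weeks". The others are ALT above 10x ULN, raised ALT with raised direct bilirubin or INR, clinical decompensation, and Investigator discretion.

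**Unscheduled testing.** Section 8.4 introduces its blood tests, HBV DNA among them, with "Obtain blood samples for the following, as applicable". It adds: "The minimum Unscheduled Visit assessments to be completed when managing ALT elevations are noted in" Section 9.10.4. In that section, the list for ALT at least 2x Baseline or nadir and above 2x ULN ends "serum albumin, INR and creatine kinase. The Investigator will determine if other Unscheduled Visit assessments should be performed". HBV DNA is not on that list. It becomes required only in the work-up of confirmed ALT above 2x Baseline or nadir and at least 10x ULN.

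**The concern.** Twelve-weekly HBV DNA suits a subject who has stayed suppressed on NrtI throughout. A restarter is different: he or she may be viremic with raised ALT, and the question at that point is whether the restarted drug is suppressing the virus again. HBV DNA answers it directly, and it is the measure in which two of the restart thresholds are written. Yet scheduled HBV DNA becomes sparser on restart, on a calendar unrelated to the restart date.

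The stake is safety monitoring of individual subjects, mainly those who restart with ALT between 2x and 10x ULN or at Investigator discretion. No planned estimate is affected. No rule in Section 4.1.2 acts on a post-restart HBV DNA value, and re-suppression after restart is not an endpoint.

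**Working it through.** The plan gives no figure for this interval, so there is none to reproduce. The check is calendar arithmetic on nominal visit weeks.

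**Inputs**
- Off-treatment visits (Table 10): 50, 52, 54, 56, 60, 64, 68, 72, 76, 80, 84, 88, 92, 96. Gaps are 2, 2, 2, then 4 weeks, so HBV DNA is never more than 4 weeks apart before restart.
- HBV DNA weeks after restart (Section 8.3.5, Table 11): 60, 72, 84, 96.
- All Table 11 visits: 52, 56, 60 and every 4 weeks to 96.

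**Formulas.** Wait = next HBV DNA week strictly after restart, minus restart week. Extra assays = later Table 11 visits that currently have no HBV DNA.

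**Restart on a scheduled visit** (Week 96 is left out because no later sample is scheduled)

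| Restart week | Wait now (weeks) | Wait if HBV DNA at every Table 11 visit (weeks) | Extra assays |
|---|---|---|---|
| 50 | 10 | 2 | 8 |
| 52 | 8 | 4 | 7 |
| 54 | 6 | 2 | 7 |
| 56 | 4 | 4 | 6 |
| 60 | 12 | 4 | 6 |
| 64 | 8 | 4 | 5 |
| 68 | 4 | 4 | 4 |
| 72 | 12 | 4 | 4 |
| 76 | 8 | 4 | 3 |
| 80 | 4 | 4 | 2 |
| 84 | 12 | 4 | 2 |
| 88 | 8 | 4 | 1 |
| 92 | 4 | 4 | 0 |
| Sum | 100 | 48 | 55 |
| Mean of 13 | 7.7 | 3.7 | 4.2 |

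The current wait is 8 weeks or more for 8 of the 13 visits.

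**By HBV DNA criterion**, taking Week 50 as the earliest visit at which HBV DNA above 2000 IU/mL could first be seen:
- ALT 5-10x ULN needs 4 weeks, so the earliest restart visit is 50 + 4 = Week 54. Over 11 visits the waits sum to 82, mean 82/11 = 7.5 weeks, with 8 weeks or more at 6 of 11. Extra assays: 40/11 = 3.6.
- ALT 2-5x ULN needs 12 weeks: 50 + 12 = 62, so the first visit is Week 64. Over 8 visits the waits sum to 60, mean 60/8 = 7.5 weeks, with 8 weeks or more at 5 of 8. Extra assays: 21/8 = 2.6.

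**Restart on any day**, counting day = 7 x week, from day 350 (Week 50) to day 671 (the day before Week 96), 322 days:
- From Week 50 to Week 60 the waits run 70, 69, ..., 1 days, summing to 70 x 71/2 = 2485.
- Each of the three 12-week blocks runs 84, 83, ..., 1 days, summing to 84 x 85/2 = 3570; three blocks give 10,710.
- Mean = (2485 + 10,710)/322 = 41.0 days = 5.9 weeks.
- Under 28 days: 4 x 27 = 108 days, 108/322 = 34%.
- 56 days or more: 15 + 3 x 29 = 102 days, 102/322 = 32%.
- With HBV DNA at every Table 11 visit: (14 x 15/2 + 11 x 28 x 29/2)/322 = (105 + 4466)/322 = 14.2 days = 2.0 weeks, maximum 4 weeks.

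**Visit windows.** Visits may move by 5 days either way. In opposite directions this stretches the longest wait from 84 to 84 + 10 = 94 days (13.4 weeks), so 12 weeks is the nominal maximum.

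**The case against.** The schedule can be defended as a consistent rule: HBV DNA is 12-weekly on NrtI and at every visit off NrtI. On-treatment sampling is at Weeks 12, 24, 36 and 48, restarters simply rejoin the on-NrtI rule, and SAP Table 3-7 has matching 12-week windows for the NrtI-Restart Phase. The consistency is real, but it treats a subject who may just have relapsed like one who never stopped.

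The stronger argument is that these subjects are already watched closely. Chemistry, coagulation, HBV TNA, HBV RNA, HBsAg and a virology back-up sample stay 4-weekly. Many restarters will meet the ALT trigger in Section 9.10.4, which covers post-treatment follow-up and leads to visits every 1 to 2 weeks at the Investigator's discretion. HBV DNA can be ordered at those visits, and the ALT-management panel in Table 12 includes it without stating a tier. All of this narrows the practical gap. It does not close it:
- The Table 12 panel refers to Section 9.10.4, where HBV DNA enters only at the confirmed 10x ULN tier.
- Only Table 9, the on-treatment schedule, has an Unscheduled Visit column marking HBV DNA; Tables 10 and 11 have none.
- TNA is an in-house assay of total HBV nucleic acids (Section 8.6.1). A low or falling value is informative, but the restart thresholds are not written in it.

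It is also fair that laboratory-triggered restarts would usually follow a visit by some days, and that the 12-week waits arise at Weeks 60, 72 and 84, when HBV DNA has just been drawn. The any-day calculation covers the first point. The second sample is taken at or before restart, so it cannot show the response to it.

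Finally, the SAP (Sections 1, 1.2 and 2.2) records termination in February 2023, after which the stopping criteria no longer applied to subjects reaching Week 48. That stands, and it limits the effect on this trial.

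**Conclusion.** The point holds as a minor one. From restart until the next of four fixed study weeks, a subject below the confirmed 10x ULN tier has no required HBV DNA. The nominal wait is 4 to 12 weeks for visit-day restarts (mean 7.7) and 1 day to 12 weeks over all days (mean 5.9, with 32% of days at 8 weeks or more), against at most 4 weeks before restart.

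These figures assume nominal visit days, equal weight for each possible restart visit or day, and no unscheduled HBV DNA. The last assumption makes them an upper description of practice, because an attentive Investigator would often order the test. The criterion-specific dates also assume that treatment had stopped and HBV DNA above 2000 IU/mL was first seen by Week 50.

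**What to change.** Add a note to protocol Section 8.3.5 and Table 11: subjects who have restarted NrtI have HBV DNA at every 4-weekly visit after restart; all other subjects on Table 11 keep Weeks 60, 72, 84 and 96. The maximum nominal wait falls to 4 weeks.

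The cost is 0 to 8 central-laboratory assays per restarted subject, averaging 4.2 over the 13 visit-day restarts. There is no added visit. There may be a small added blood volume, since tube details are in the Laboratory Manual. The SAP needs no change: its windows for this phase are already anchored to the restart date (Sections 3.6.4 and 3.6.5), and the rule in Section 3.6.6 selects the record nearest the nominal day. With this trial terminated, the main value of the note is for any later protocol that reuses the stop-and-restart design.
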